5.2 Eliciting and Reporting Adverse Events

The investigator or subinvestigator will periodically assess subjects for the occurrence of AEs. To avoid bias in eliciting AEs, subjects should be asked the nonleading question: "How have you felt since your last visit?" For all AEs (serious and nonserious) reported by the subject, the event name, start and stop dates, severity, seriousness, relationship to IMP, actions taken regarding IMP administration, and outcome thereof must be recorded in the source documents and CRFs provided by the sponsor. Adverse event and SAE collection is to begin after a subject has signed the ICF. In this trial, AEs occurring during the screening period and the antidepressant treatment period (Phase A) will be assessed in comparison to the subject's condition at screening, and AEs occurring during the double-blind period (Phase B) and the antidepressant-responder treatment-continuation period (Phase A+) will be assessed in comparison to the subject's condition at Week 8 of the antidepressant treatment period (Phase A).

Use medical terminology in AE reporting. Adverse events should be reported as a single unifying diagnosis whenever possible or, in the absence of a unifying diagnosis, as individual signs or symptoms. Exacerbation or disease progression should be reported as an AE only if there are unusual or severe clinical features that were not present, or experienced earlier, or not expected based on the course of the condition. If a reported AE has worsened in severity or seriousness, it should be reported as a new AE on the CRF.

In addition, the sponsor must be notified immediately by e-mail, in principle, of any IREs according to the procedure outlined below, in Section 5.3 Immediately Reportable Events. Special attention should be paid to recording hospitalization and concomitant medications.

5.3 Immediately Reportable Events

The investigator or subinvestigator must report any SAE, potential DILI, or confirmed pregnancy to the sponsor by e-mail (using the contact information on the title page of this protocol) immediately after either the investigator, subinvestigator, or designee becomes aware of the event. The IRE form and so on should be completed and sent by e-mail, in

principle, to the sponsor. Please note that the IRE form is NOT the AE section of the CRF. Due consideration must be given to privacy when the IRE form and so on is sent by mail or other means of communication.

For subjects experiencing SAEs or IREs, such AEs should be followed until the events are resolved or stabilized, or the subject is lost to follow-up or has died. *Resolved* means that the subject has returned to the baseline state of health, and *stabilized* means that the investigator or subinvestigator does not expect any further improvement or worsening of the subject's condition. It is expected that the investigator or subinvestigator will provide or arrange appropriate supportive care for the subject and will provide prompt updates on the subject's status to the sponsor.

5.4 Potential Drug-induced Liver Injury

For a subject who experiences an elevation in aspartate aminotransferase (AST) or alanine aminotransferase (ALT) that is ≥ 3 times the upper limit of normal (ULN), total bilirubin level should also be evaluated. If the total bilirubin is ≥ 2 times the ULN, complete the IRE form and so on with all values listed and also report as an AE in the source documents and CRF.

5.5 Pregnancy

Women of childbearing potential (WOCBP) are defined as female subjects for whom menstruation has started and who are not documented as sterile (ie, have had a bilateral oophorectomy and/or hysterectomy or who have been postmenopausal for at least 12 months).

For WOCBP and for men who are sexually active, there must be a documented agreement that the subject and/or their partner will take effective measures (ie, double-barrier method) to prevent pregnancy during the course of the trial and for 30 days after the last dose of IMP. Unless the subject or their partner is sterile (ie, women who have had a bilateral oophorectomy and/or hysterectomy or who have been postmenopausal for at least 12 consecutive months; or men who have had a bilateral orchidectomy) or remains abstinent, 2 of the following precautions must be used: vasectomy, tubal ligation, vaginal diaphragm, intrauterine device, oral contraceptives, or condom with spermicide. Any single method of birth control, including vasectomy and tubal ligation, may fail, leading to pregnancy. The contraceptive method will be documented at each trial visit.

Protocol 331-102-00058

Before enrolling WOCBP in this clinical trial, investigators or subinvestigators must review the below guidelines about trial participation with all WOCBP. The topics should generally include:

- General information
- Informed consent form
- Pregnancy prevention information
- Drug interactions with hormonal contraceptives
- Contraceptives in current use
- Guidelines for the follow-up of a reported pregnancy

Before trial enrollment, WOCBP must be advised of the importance of avoiding pregnancy during trial participation and the potential risk factors for an unintentional pregnancy. The subject must sign an informed consent form stating that the abovementioned risk factors and the consequences were discussed with her.

During the trial, all WOCBP should be instructed to contact the investigator or subinvestigator immediately if they suspect they might be pregnant (eg, missed or late menstrual cycle).

If a subject is suspected to be pregnant before she receives IMP, the IMP administration must be withheld until the results of pregnancy tests are available. If the pregnancy is confirmed, the subject must not receive the IMP and must not be enrolled in the trial. If pregnancy is suspected while the subject is taking IMP, the IMP must be withheld immediately (if reasonable, taking into consideration any potential withdrawal risks) until the result of the serum pregnancy test is known. If pregnancy is confirmed, the IMP will be permanently discontinued in an appropriate manner (eg, dose tapering if necessary for subject safety) and the subject will be withdrawn from the trial.

The investigator or subinvestigator must immediately notify the sponsor of any pregnancy associated with IMP exposure during the trial and for 30 days after the last dose of IMP, and record the event on the IRE form, and forward it to the sponsor. The sponsor will forward Pregnancy Surveillance Form(s) for monitoring the outcome of the pregnancy.

Protocol-required procedures for trial discontinuation and follow-up must be performed on the subject unless contraindicated by pregnancy (eg, x-ray studies). Other appropriate pregnancy follow-up procedures should be considered, if indicated. In addition, the investigator or subinvestigator must report to the sponsor, on appropriate Pregnancy Surveillance Form(s), follow-up information regarding the course of the pregnancy,

including perinatal and neonatal outcome. Infants will be followed for a minimum of 6 months from the date of birth.

5.6 Procedure for Breaking the Blind

In an emergency situation, such as when a subject experiences an SAE, if breaking the treatment assignment code is considered necessary by the investigator or subinvestigator to ensure the subject's safety, the investigator or subinvestigator will be able to obtain the emergency code break information through IWRS in accordance with the separately specified procedures. The investigator or subinvestigator must contact the sponsor within 24 hours of opening the code, and prepare a document containing the reason and process of opening the code and submit it to the sponsor. If the blind is broken, the Department of Pharmacovigilance must be notified immediately (see the cover page of this protocol for contact information). Documentation of breaking the blind should be recorded in the subject's medical record with the date and time the blind was broken and the names of the personnel involved. Once the blind is broken for a subject, the IMP may not be reinitiated for that subject.

5.7 Follow-up of Adverse Events

5.7.1 Follow-up of Nonserious Adverse Events

Nonserious AEs that are identified at any time during the trial must be recorded in the source documents and the AE section of the CRF, with the current status (ongoing or resolved/recovered) noted. All nonserious events (other than immediately reportable events) that are ongoing at the end of trial date (final day of observation) will be recorded as ongoing in the source documents and CRF. For any AE having been identified throughout the trial, during data analysis, additional relevant medical history information may be requested by the sponsor to further ascertain causality (including, but not limited to, information such as risk-related behavior, family history and occupation). The follow-up information after the end of trial date (final day of observation) will be recorded in the subject's medical record.

5.7.2 Follow-up of Serious Adverse Events and Immediately Reportable Events

This trial requires that subjects be actively monitored for SAEs and IREs up to 30 days (±5 days) after the final day of IMP administration (end of trial date [final day of observation]).

Serious AEs and IREs that are identified or ongoing at the end of trial date must be recorded in the source documents and the AE section of the CRF. Between the end of

trial date for the individual subject and the end of trial date for the last subject, if any new information regarding an SAE or IRE becomes available (eg, the event is resolved), this must be reported to the sponsor using the IRE form and so on, and the information must be recorded in the source documents and the AE section of the CRF. The investigator or subinvestigator will follow SAEs and IREs, and will continue to report any significant information to the sponsor until the events are resolved or stabilized, or the subject is lost to follow-up or has died, using the IRE form and so on.

5.7.3 Follow-up and Reporting of Serious Adverse Events and Immediately Reportable Events Occurring After the End of Trial Date (Final Day of Observation)

Any new SAEs or IREs reported to the investigator or subinvestigator, which occur after the end of trial date (final day of observation) and are determined by the investigator or subinvestigator to be associated with the use of the IMP, should be reported to the sponsor. This includes SAEs and IREs that are captured on follow-up telephone contact or at any other time point after the defined trial period. The investigator or subinvestigator will follow SAEs and IREs identified after the defined trial period and continue to report any significant follow-up information to the sponsor until the events are resolved or stabilized, or the subject is lost to follow-up or has died, using the IRE form and so on.

6 Pharmacokinetic/Pharmacogenomic/ Analysis

6.1 Pharmacokinetic Analysis Methods

Descriptive statistics of plasma brexpiprazole concentrations will be determined for each treatment group.

6.2 Pharmacogenomic Analysis Methods

A list of data obtained from CYP2D6 genetic assessment will be provided without summarization.

6.3

7 Statistical Analysis

For the double-blind period (Phase B), the definitions of the datasets for analysis and the analysis methods for the specified endpoints are described below.

The detailed statistical analysis plan for the double-blind period (Phase B) and the analysis plans for the antidepressant treatment period (Phase A) and the antidepressant-responder treatment-continuation period (Phase A+) are described in a separate Statistical Analysis Plan. The Statistical Analysis Plan will be finalized prior to data lock.

7.1 Determination of Sample Size

In phase 3, double-blind, placebo-controlled, fixed dose trials of brexpiprazole (331-10-227, 331-10-228, and 331-13-214) conducted outside Japan, changes from baseline in MADRS total scores at Week 6 of the double-blind period (Phase B) have been analyzed by the Mixed-model Repeated Measure (MMRM) method (for 331-10-227 and 331-10-228, based on the results for efficacy from an analysis of subgroups meeting the inclusion criteria that had been revised in the middle of the trials), which demonstrated that the differences between the brexpiprazole groups (the 3 mg group in 331-10-227, and the 2 mg group in 331-10-228 and 331-13-214) and the placebo group were -1.9, -3.2, and -2.3, respectively, and that the standard deviations obtained from standard errors and numbers of subjects at Week 6 of the double-blind period (Phase B) were 7.2, 7.7 and 8.2, respectively. On the assumption that the difference in changes from baseline in MADRS total scores at Week 6 of the double-blind period (Phase B) is -2.4 for the brexpiprazole group compared with the placebo group with a standard deviation of 7.7, this trial will require 218 subjects per group to ensure a power of 90% in a two-sided test with a significance level of 0.05. We have decided that the planned number of subjects for randomization will be 240 per group, assuming that 7% of subjects will discontinue the trial during the double-blind period (Phase B) and some subjects will be excluded from analysis.

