In phase 3, double-blind, placebo-controlled trials of fixed doses of brexpiprazole (331-10-227, 331-10-228, and 331-13-214) conducted outside Japan, changes from baseline in MADRS total scores at Week 6 of the double-blind period (Phase B) have been analyzed by the MMRM method (for 331-10-227 and 331-10-228 trials, based on the results for efficacy from an analysis of subgroups meeting the inclusion criteria that had been revised in the middle of the trials). which demonstrated that the differences between the brexpiprazole groups (the 3 mg group in 331-10-227 trial, and the 2 mg group in 331-10-228 and 331-13-214 trials) and the placebo group were -1.9, -3.2, and -2.3, respectively, and that the standard deviations obtained from standard errors and numbers of subjects at Week 6 of the double-blind period (Phase B) were 7.2, 7.7, and 8.2, respectively. On the assumption that the difference in changes from baseline in MADRS total scores at Week 6 of the double-blind period (Phase B) is -2.4 for the brexpiprazole group compared with the placebo group with a standard deviation of 7.7, this trial will require 218 subjects per group to ensure a power of 90% in a twosided test with a significance level of 0.05. We have decided that the planned number of subjects for randomization will be 240 per group, assuming that 7% of subjects will discontinue the trial during the double-blind period (Phase B) and some subjects will be excluded from analysis.

Trial Duration: 01 Jun 2018 to 31 Jul 2022 (planned)

Table of Contents

| Protocol Synopsis | | 2 |
|-------------------|--|----|
| Table | of Contents | 13 |
| List of | In-text Tables | 19 |
| | In-text Figures | |
| | Appendices | |
| | Abbreviations and Definitions of Terms | |
| 1 | Introduction | |
| 1.1 | Nonclinical Data | |
| 1.2 | Clinical Data | |
| 1.2.1 | Clinical Data From Japanese Trials in Subjects With Schizophrenia | |
| 1.2.1.1 | Dose-finding Trial in Subjects With Schizophrenia (331-10-002) | 28 |
| 1.2.1.2 | Long-term Trial in Subjects With Schizophrenia (331-10-003) | 29 |
| 1.2.2 | Clinical Data From Overseas Trials in Subjects With Major Depressive Disorder | 29 |
| 1.2.2.1 | Confirmatory Trial in Subjects With Major Depressive Disorder (331-10-227) | 29 |
| 1.2.2.2 | Confirmatory Trial in Subjects With Major Depressive Disorder (331-10-228) | 30 |
| 1.2.2.3 | Confirmatory Trial in Subjects With Major Depressive Disorder (331-13-214) | 31 |

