1.2.2 Clinical Data From Overseas Trials in Subjects With Major Depressive Disorder

1.2.2.1 Confirmatory Trial in Subjects With Major Depressive Disorder (331-10-227)

A double-blind, placebo-controlled trial was conducted outside Japan to evaluate the efficacy, safety, and tolerability of fixed doses of brexpiprazole in subjects with major depressive disorder who had an insufficient response to antidepressant therapy. All eligible subjects who passed the screening test entered an 8-week antidepressant treatment period (Phase A) in which SSRI/SNRI and placebo were administered in a single-blind manner. Subjects who responded to SSRI/SNRI and placebo in Phase A

entered a 6-week antidepressant-responder treatment-continuation period (Phase A+) in which SSRI/SNRI and placebo continued to be concomitantly administered for another 6 weeks. Subjects who had an insufficient response to SSRI/SNRI and placebo in Phase A entered a double-blind period (Phase B) in which brexpiprazole or placebo was administered concomitantly with SSRI/SNRI for 6 weeks in a double-blind manner. This trial had a total of 3 treatment groups consisting of a placebo group and 2 fixed-dose groups of brexpiprazole (1 and 3 mg/day). The change from baseline to Week 6 in the Montgomery Asberg Depression Rating Scale (MADRS) total score, the primary endpoint, showed numerical improvement in the 3-mg group compared with the placebo group (LSMD: -1.52, p = 0.0327). Improvement in the MADRS total score was numerically greater in the 1-mg group than in the placebo group (LSMD: -1.19, p = 0.0925). In the efficacy data from a subgroup meeting the inclusion criteria revised during the trial, the change from baseline to Week 6 in the MADRS total score showed improvement in the 3-mg group compared with the placebo group (LSMD: -1.95, p = 0.0079). Meanwhile, the change from baseline in the 1-mg group was -1.30(p = 0.0737).

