7.4 Primary and Secondary Endpoint Analyses

7.4.1 Primary Endpoint Analyses

The primary endpoint is mean changes from baseline (Week 8 of the antidepressant treatment period [Phase A]) in MADRS total scores at Week 6 of the double-blind period (Phase B).

For the primary analysis, MMRM analysis will be performed using the OC data set in the FAS. The statistical hypotheses will be tested, based on differences in least square means between each brexpiprazole group and the placebo group, which are calculated by MMRM. To adjust for multiplicity of tests, due to there being 2 comparisons with the placebo group for each of the brexpiprazole groups, a fixed-sequence approach will be used to control overall type 1 error rates. Comparison between the brexpiprazole 2 mg/day group and placebo group will be performed first; only when significance is observed at a two-sided significance level of 5%, will comparison between the brexpiprazole 1 mg/day group and placebo group be performed at a two-sided significance level of 5%.

The MMRM will include treatment group (brexpiprazole 1 mg/day group, brexpiprazole 2 mg/day group, and placebo group), time point (double-blind period [Phase B] Weeks 1, 2, 3, 4, 5, and 6), and interaction between treatment group and time point as factors, and baseline and interaction between baseline and time point as covariates. Unstructured error

variance-covariance structure will be assumed. For a degree-of-freedom approximation, the Kenward-Roger method will be used. If any problems in convergence status arise in the estimation of variance components, heterogeneous Toeplitz, heterogeneous autoregressive of order 1, and heterogeneous compound symmetry, which are error variance-covariance structures, will be applied in this order, and the first structure that achieves convergence will be used in the primary analysis. If anything other than an unstructured variance-covariance structure is selected, a sandwich estimator for standard errors will be used.

For each time point, least square means of each treatment group and differences in least square means between each brexpiprazole group and the placebo group, as well as the two-sided 95% confidence intervals (CIs) will be determined.

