3.5.8 Abnormal Involuntary Movement Scale (AIMS)

The AIMS total score will be the sum of scores for AIMS items 1 through 7.

4 Sample Size

In phase 3, double-blind, placebo-controlled, fixed dose trials of brexpiprazole (331-10-227, 331-10-228, and 331-13-214) conducted outside Japan, changes from baseline in MADRS total scores at Week 6 of the double-blind period (Phase B) have been analyzed by the Mixed-model Repeated Measure (MMRM) method (for 331-10-227 and 331-10-228, based on the results for efficacy from an analysis of subgroups meeting the inclusion criteria that had been revised in the middle of the trials), which demonstrated that the differences between the brexpiprazole groups (the 3 mg group in 331-10-227, and the 2 mg group in 331-10-228 and 331-13-214) and the placebo group were -1.9 , -3.2 , and -2.3 , respectively, and that the standard deviations obtained from standard errors and numbers of subjects at Week 6 of the double-blind period (Phase B) were 7.2, 7.7, and 8.2, respectively. On the assumption that the difference in changes from baseline in MADRS total scores at Week 6 of the double-blind period (Phase B) is -2.4 for the brexpiprazole group compared with the placebo group with a standard deviation of 7.7, this trial will require 218 subjects per group to ensure a power of 90% in a two-sided test with a significance level of 0.05. We have decided that the planned number of subjects for randomization will be 240 per group, assuming that 7% of subjects will discontinue the trial during the double-blind period (Phase B) and some subjects will be excluded from analysis.

5 Statistical Analysis Datasets

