8.1.1 Primary Efficacy Analysis

For the primary analysis, MMRM analysis will be performed using the OC data set in the FAS. The statistical hypotheses will be tested, based on differences in least square means between each brexpiprazole group and the placebo group, which are calculated by MMRM. To adjust for multiplicity of tests, due to there being 2 comparisons with the placebo group for each of the brexpiprazole groups, a fixed-sequence approach will be used to control overall type 1 error rates. Comparison between the brexpiprazole 2 mg/day group and placebo group will be performed first; only when significance is observed at a two-sided significance level of 5%, will comparison between the brexpiprazole 1 mg/day group and placebo group be performed at a two-sided significance level of 5%.

The MMRM will include treatment group (brexpiprazole 1 mg/day group, brexpiprazole 2 mg/day group, and placebo group), time point (double-blind period [Phase B] Weeks 1, 2, 3, 4, 5, and 6), and interaction between treatment group and time point as factors, and baseline and interaction between baseline and time point as covariates. Unstructured error variance-covariance structure will be assumed. For a degree-of-freedom approximation,

the Kenward-Roger method will be used. If any problems in convergence status arise in the estimation of variance components, heterogeneous Toeplitz, heterogeneous autoregressive of order 1, and heterogeneous compound symmetry, which are error variance-covariance structures, will be applied in this order, and the first structure that achieves convergence will be used in the primary analysis. If anything other than an unstructured variance-covariance structure is selected, a sandwich estimator for standard errors will be used.

For each time point, least square means of each treatment group and differences in least square means between each brexpiprazole group and the placebo group, as well as the two-sided 95% confidence intervals (CIs) will be determined.

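### Does the single 90% power figure mislead, given that 1 mg is tested only after 2 mg succeeds?

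*Protocol*

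**What the plan says.** Protocol 7.1 assumes that the Week 6 difference in MADRS change "is -2.4 for the brexpiprazole group compared with the placebo group with a standard deviation of 7.7". On that basis "this trial will require 218 subjects per group to ensure a power of 90% in a two-sided test with a significance level of 0.05". The Synopsis and SAP 4 (Sample Size) repeat the calculation. The inputs are the overseas results for "the 3 mg group in 331-10-227, and the 2 mg group in 331-10-228 and 331-13-214": differences of -1.9, -3.2 and -2.3, with SDs of 7.2, 7.7 and 8.2. The number randomized is raised to 240 per group for 7% discontinuation and some exclusions.

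The testing order is set elsewhere. SAP 8.1.1 says "Comparison between the brexpiprazole 2 mg/day group and placebo group will be performed first". Under Protocol 7.4.1, "only when significance is observed at a two-sided significance level of 5%, will comparison between the brexpiprazole 1 mg/day group" and placebo be made, also at 5%.

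On 1 mg, Protocol 1.2.2.1 reports from the revised-criteria subgroup of 331-10-227 that "the change from baseline in the 1-mg group was -1.30" (p = 0.0737). Despite the wording, this reads as a difference from placebo: it carries a p-value and follows the 3 mg difference of -1.95. The same section gives -1.19 (p = 0.0925) for the primary analysis. Protocol 2.4.2.1 says that 1 mg was not confirmed overseas and is included to learn whether it is the lowest dose that works in Japanese patients.

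**The concern.** There are two confirmatory comparisons and one power figure, attached to a brexpiprazole group whose dose is not named. Because 1 mg is tested only after 2 mg succeeds, the chance of declaring 1 mg effective must be below 90% at 218 per group, even if both doses have the assumed effect. The assumed effect also comes only from 2 mg and 3 mg arms, while the protocol's own 1 mg estimates are about half as large.

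The trial's objective includes dosage, and the question about 1 mg is answered by the second test. A reader who met a non-significant 1 mg result and judged it against 90% might take it as good evidence that 1 mg does not work.

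**Working it through.** **Inputs.** Difference 2.4, SD 7.7, two-sided 0.05 and 218 per group (Protocol 7.1); 240 randomized per group with 7% discontinuation, so 240 × 0.93 = 223 completers; 1:1:1 allocation (Protocol 3.6); 1 mg difference 1.30 as a weaker scenario (Protocol 1.2.2.1). Signs are dropped below.

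**1. The plan's own figure.** The normal approximation gives n = 2 × (1.960 + 1.282)² × (7.7/2.4)² = 216.3, so 217. The two-sample t test has power 0.8996 at 217 and 0.9009 at 218. The plan's 218 is therefore exact for one pairwise comparison.

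**2. Single-test power.** The standard error is 7.7 × √(2/n). At n = 218 it is 0.7375, so 2.4/0.7375 = 3.254 and power = Φ(3.254 − 1.960) = 90.2% (90.1% with the t distribution).

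**3. Power through the sequence.** The two test statistics share the placebo arm. Their covariance is σ²/n and each variance is 2σ²/n, so the correlation is 0.5. The probability of declaring 1 mg effective is the probability that both tests reject in favour of the drug, taken from a bivariate normal with 2 mg at 2.4:

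| Evaluable per group | One test alone at 2.4 | Both tests, 1 mg at 2.4 | 1 mg alone at 1.30 | 1 mg through the sequence at 1.30 |
|---|---|---|---|---|
| 218 | 90.2% | 83.6% | 42.2% | 41.1% |
| 223 | 90.8% | 84.5% | 43.0% | 41.9% |
| 240 | 92.7% | 87.5% | 45.6% | 44.8% |

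Simulation with pooled variance and t critical values (400,000 replicates) gives 83.5%, 84.3% and 87.4% for the third column. Since the MMRM uses partial data, the effective n lies between 223 and 240 before other exclusions.

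**4. What the sequence costs.** At 2.4 the loss is 90.2 − 83.6 = 6.6 points at 218 and 92.7 − 87.5 = 5.2 points at 240. At 1.30 it is 42.2 − 41.1 = 1.1 points at 218 and 45.6 − 44.8 = 0.8 points at 240. The low figures at 1.30 come almost entirely from the smaller effect.

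**5. Sensitivity at n = 218.** Over the plan's source SDs of 7.2 to 8.2, the single test at 2.4 runs from 93.5% down to 86.2%, a swing of 7.3 points, slightly more than the sequence costs. Both tests at 2.4 run from 88.9% to 77.7%; 1 mg at 1.30 through the sequence runs from 46.3% to 36.6%. With 1.19 at SD 7.7, the sequence gives 35.6% (218) to 38.9% (240).

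**6. How firm the 1.30 is.** p = 0.0737 corresponds to z = 1.788, so SE = 1.30/1.788 = 0.727 and the 95% CI is about -2.72 to +0.12. That interval includes -2.4.

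**The case for a change.** The strongest case for a change is that sizing only the first test is acceptable, but the plan should then say so. As written, the 90% belongs to no named dose, and a reader interested in 1 mg has no other figure. Full use of all 240 still gives only 87.5% for both doses at the plan's own assumption. The plan also took the 3 mg result from the 331-10-227 subgroup for its sizing and left out the 1 mg result reported beside it.

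The observation stands: neither document gives 1 mg power or joint power, and naming the dose would have been clearer. The conclusion does not follow. Protocol 7.1 claims 90% for one two-sided test and nowhere extends it to 1 mg or to both doses. The facts a reader needs are in the protocol: the source arms are named as 2 mg and 3 mg, the 1 mg estimates are reported, and 1 mg is described as unconfirmed. Protocol 2.4.2.1 also gives grounds for testing it, namely an advantage over placebo at p < 0.05 in Weeks 1 through 5 and Week 6 response and remission rates not markedly different from 3 mg. A non-significant 1 mg result would be read with its planned estimate and 95% confidence interval, which show directly what has and has not been excluded.

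**Conclusion.** No change is needed. The 218 and the 90% are right for the comparison they describe, and the design delivers that power for 2 mg against placebo. Type I error is controlled by the fixed sequence. What is missing is a planning figure for the second test: about 84% to 87.5% if both doses have -2.4 with SD 7.7. Adding it would alter no sample size, significance level, testing order, analysis or conclusion.

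Sizing on the first test and accepting somewhat lower power for the second is a fair trade-off. About 258 evaluable per group would be needed for 90% on both doses at -2.4. The 41% to 45% at -1.30 is an effect-size scenario from one imprecise subgroup estimate and not a fault of the multiplicity procedure, which costs about 1 point there.

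These figures assume 2 mg at -2.4, a common SD, correlation 0.5 and no gain from earlier visits in the MMRM, a gain that the plan's own calculation also leaves out.
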